AED = anti-epileptic drug; BID = twice daily; BZD = benzodiazepine; CGI-I = Clinical Global Impression-Improvement; CGI-S = Clinical Global Impression – Severity of Symptoms; C-SSRS = Columbia-Suicide Severity Rating Scale; CT = computed tomography; ECG = electrocardiogram; ET = Early Termination; HBV = hepatitis B virus; HCG = human chorionic gonadotropin; HCV = hepatitis C virus; HIV = human immunodeficiency virus; ICF = informed consent form; IMP = investigational medicinal product; mCIWA-B = Modified Clinical Institute Withdrawal Assessment – Benzodiazepines; MRI = magnetic resonance imaging; PGIC = Patient Global Impression of Change; PK = pharmacokinetic; QOLIE-31 = Quality of Life in Epilepsy-31; SIF/DRF = Seizure Identification and Diagnostic Review Form; TESC = The Epilepsy Study Consortium.

- a. Individual sites may require subjects to have COVID-19 testing done prior to randomization. COVID-19 testing may be performed after randomization per the investigator's discretion.
- b. Contact with subject via phone call or other means of communication to check on their status.
- c. In the event that a subject is unable to attend a clinic visit in person due to restrictions related to COVID-19, this visit may be completed remotely. Please refer to the Trial Operations Manual for further instructions related to remote visits.
- d. At Visit 4, the investigator will evaluate the subject's eligibility to continue treatment with CVL-865 in the open-label extension trial CVL-865-SZ-002. If the investigator determines the subject is eligible for the trial, he/she will discuss with the subject if they would like to continue into Trial CVL-865-SZ-002. If the investigator determines the subject is eligible and the subject agrees to continue participation in Trial CVL-865-SZ-002, consent will be obtained and unique procedures for Visit 1 of Trial CVL-865-SZ-002 will be completed. Subjects who do not continue into Trial CVL-865-SZ-002 will begin the Taper Phase.

- e. Subjects who require early termination should begin the Taper Period at the time the decision is made to discontinue. All indicated procedures should be performed per protocol. If a subject discontinues early and it is inadvisable for them to taper IMP (after agreement from medical monitor), the subject should complete Visit 6 assessments approximately 30 days following the last dose of IMP.

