4. DATA CONVENTIONS AND VISIT WINDOWS

4.1. Data Conventions

4.1.1. Age

Age is the age at the time of informed consent and is as captured on the eCRF (note: date of birth is not captured on the eCRF).

4.1.2. Day 1

Day 1 is the day IMP is first initiated.

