4.1.3. Study Day of an Event

Study day of an event is defined relative to Day 1 as:

Study $Day = event date - date of Day 1 (+ 1, if event date \ge date of Day 1)$.

This calculation will result in negative study days for an event occurring prior to the start of IMP and positive study days for an event on or after the start of IMP. There will be no Day 0 value to match the schedule of events.

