4.3. Visit Windows

Data collected longitudinally across visits will be summarized and analyzed by visit. Visits will be presented according to the nominal study day and visit as obtained from the eCRF or laboratory data unless the visit is an early termination or unscheduled visit. Early termination and unscheduled visits will be assigned visit windows based on the study day completed according to Table 4 -Table 9.

If assessments are collected multiple times within a given visit, the scheduled visit, if available, will be used for summary presentations. If no scheduled visit is available, then the result closest to the scheduled visit date will be used for summary presentations. If two unscheduled measurements (discharge or unscheduled visit) have the same distance to the expected date, the earlier value will be used. If a subject has multiple non-missing unscheduled values on the same date, then the last one is used, as determined by the time collected, if available.

Table 4:Visit Windows for Early Termination and Unscheduled Visits - ECGs and
Vital Signs

Study Day of Early Termination or Unscheduled Visit	Analysis Visit	Analysis Visit Target Day
1 (pre-dose) or earlier	Baseline	
1* to 15	Day 1 (Visit 1)	1
16 to 57	Day 43 (Visit 3)	43
58 to 82	Day 71 (Visit 4)	71
83 to 106	Day 92 (Visit 5)	92
107 and higher	Day 120 (Visit 6)	120

*Only post-dose values at Day 1 will be windowed to Day 1.

Table 5:Visit Windows for Early Termination and Unscheduled Visits - Safety Labs
and C-SSRS

Study Day of Early Termination or Unscheduled Visit	Analysis Visit	Analysis Visit Target Day
1 or earlier	Baseline	
2 to 8	Day 1 (Visit 1)	1
9 to 29	Day 15 (Visit 2)	15
30 to 57	Day 43 (Visit 3)	43
58 to 82	Day 71 (Visit 4)	71
83 to 106	Day 92 (Visit 5)	92
107 and higher	Day 120 (Visit 6)	120

Table 6: Visit Windows for Early Termination and Unscheduled Visits – CGI-S

Study Day of Early Termination or Unscheduled Visit	Analysis Visit	Analysis Visit Target Day
1 or earlier	Baseline	
2 to 8	Day 1 (Visit 1)	1
9 to 29	Day 15 (Visit 2)	15
30 to 57	Day 43 (Visit 3)	43
58 or higher	Day 71 (Visit 4)	71

Table 7:Visit Windows for Early Termination and Unscheduled Visits – PGIC and
CGI-I

Study Day of Early Termination or Unscheduled Visit	Analysis Visit	Analysis Visit Target Day
29 or earlier	Day 15 (Visit 2)	15
30 to 57	Day 43 (Visit 3)	43
58 or higher	Day 71 (Visit 4)	71

Table 8:Visit Windows for Early Termination and Unscheduled Visits – QOLIE-31
and HUI

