Study Day of Early Termination or Unscheduled Visit	Analysis Visit	Analysis Visit Target Day
1 or earlier	Baseline	
2 or greater	Day 71 (Visit 4)	71

Table 9:Visit Windows for Early Terminations and Unscheduled – mCIWA-B

Study Day of Early Termination or Unscheduled Visit	Analysis Visit	Analysis Visit Target Day
1 to 74 (on treatment, prior to Taper Phase)	Baseline	
1 to 82 (off treatment)	Day 78 (Contact)	78
83 to 89	Day 85 (Contact)	85
90 to 96	Day 92 (Visit 5)	92
97 to 110	Day 99 (Contact)	99
110 and higher	Day 120 (Visit 6)	120

Cerevel

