5.14.8. Modified Clinical Institute Withdrawal Assessment – Benzodiazepines (mCIWA-B)

The clinician-observed assessment section has been removed for the modified version of Clinical Institute Withdrawal Assessment – Benzodiazepines (CIWA-B), and the total scores of mCIWA-B ranges from 1 to 68. The total score will be summarized descriptively at the scheduled visits and contacts by treatment group in addition to change from last on treatment assessment prior to or on Day 71 (Visit 4).

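### SAP Table 9 places early-termination and unscheduled mCIWA-B scores by days since first dose rather than time since dose reduction, so the Day 78 row mixes unlike times and some taper scores have no clear row

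*SAP*

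**What the plan says.** The clock is the first dose. SAP 4.1.2 states that "Day 1 is the day IMP is first initiated", and SAP 4.1.3 counts study days from there. SAP 4.3 then says "Early termination and unscheduled visits will be assigned visit windows based on the study day completed according to Table 4 -Table 9". Every other visit keeps its nominal eCRF label. If several results fall in one visit, the scheduled one is used; "If no scheduled visit is available, then the result closest to the scheduled visit date will be used for summary presentations".

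For mCIWA-B, Table 9 has two rows that depend on treatment status. "1 to 74 (on treatment, prior to Taper Phase" maps to Baseline and "1 to 82 (off treatment" maps to the Day 78 contact. The remaining rows use study day alone: 83 to 89 (Day 85), 90 to 96 (Day 92), 97 to 110 (Day 99), and 110 and higher (Day 120).

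On early stopping, footnote e of the Schedule of Assessments says "Subjects who require early termination should begin the Taper Period at the time the decision is made to discontinue". SAP Table 3 starts the Taper Phase on the early-termination date itself. A subject for whom tapering is inadvisable has Visit 6 assessments about 30 days after the last dose.

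SAP 5.14.8 sets the analysis: "The total score will be summarized descriptively at the scheduled visits and contacts by treatment group", together with change from the last on-treatment assessment on or before Day 71. The schedule lists mCIWA-B at Visit 4, the taper and follow-up contacts, Visit 5, Visit 6 and the ET visit, and at no scheduled visit before Visit 4.

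**The concern.** A withdrawal scale is interpretable against the time since the dose began to fall or dosing stopped. For a completer who tapers, study day carries that information, because the taper follows Visit 4. For an early terminator it does not, because the taper can begin on any day. Windowing by study day therefore puts scores from very different points after dose reduction under one label.

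Withdrawal symptoms on the mCIWA-B are a named secondary safety endpoint in both documents. What is at stake is whether the by-visit profile and the change score describe withdrawal at a known time, and whether an early terminator has a usable reference value for the change score.

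**Working it through.** The plan states no figure on this point to reproduce. The check applies Table 9 as written to hypothetical stopping days, for ET and unscheduled records only.

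**Inputs.** Study day from first dose (SAP 4.1.2, 4.1.3); Table 9 rows (SAP 4.3); taper start on Day 71 for completers or on the ET date (SAP Table 3); 3-week taper, taken as 21 days (SAP 1.1).

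**1. Off-drug scores in the Day 78 row.** The row accepts Days 1 to 82. The longest time off drug it admits is 82 − day of last dose:
- last dose Day 14: 82 − 14 = 68, so 1 to 68 days off drug
- last dose Day 28: 82 − 28 = 54, so 1 to 54 days
- last dose Day 43: 82 − 43 = 39, so 1 to 39 days
- last dose Day 70: 82 − 70 = 12, so 1 to 12 days

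For a completer under Table 3, Day 78 is 78 − 71 = 7 days after taper start. Days 75 to 82, which follow the end of the Baseline row, are 4 to 11 days after it. So an unscheduled score on Day 58, 30 days after a last dose on Day 28, is labelled as the Day 78 contact. The same score entered as nominal Visit 6 stays at Visit 6.

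**2. Scores on taper drug before Day 83.** Read literally, a subject on taper drug is not before the Taper Phase and is not off treatment, so neither of the first two rows applies. A taper starting on Day s covers Days s to s + 20:
- s ≤ 62: s + 20 ≤ 82, so all 21 taper days have no row
- s = 63: only Day 83 is covered, so 20 of 21 have no row
- s = 70: Days 70 to 82, so 13 of 21 have no row

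If off treatment instead means off the maintenance dose, these days do have a row, but it is always Day 78. For a taper starting on Day 29, scores 7, 14 and 20 days in (Days 36, 43 and 49) all go to Day 78. So do later off-drug scores up to Day 82, which is 82 − 29 = 53 days after taper start.

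**3. Rows from Day 83.** These carry no treatment status. A subject who stopped without taper on Day 57 and has an unscheduled score on Day 87 (30 days off drug) goes to the Day 85 row. For a completer that row is 85 − 71 = 14 days into the taper.

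**4. Day 110.** It satisfies both 97 to 110 and 110 and higher.

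**5. The ET score.** ET visits are explicitly windowed. Because Table 3 makes the ET date the first taper day, a score taken at that visit is not clearly before the Taper Phase. With no mCIWA-B scheduled before Visit 4, it is often the only possible on-treatment reference for a subject who stops before then. If it is not Baseline, that subject may have no reference for the change in SAP 5.14.8.

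**6. Scale.** The planned 150 randomized and 120 evaluable imply up to 150 − 120 = 30 early terminators, about 10 per arm. The documents do not say how many will have ET or unscheduled mCIWA-B scores, or whether contacts after early termination are entered under nominal labels.

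**The case against.** The strongest reply is that Table 9 touches few records. Only ET and unscheduled visits are windowed. An early terminator who tapers from Day 36 would, using the completer's offsets of 7, 14, 21, 28 and 49 days from Day 71, be seen on Days 43, 50, 57, 64 and 85. Those are that subject's own contacts, Visit 5 and Visit 6. Entered under those labels, none is re-windowed, and scheduled records take priority over unscheduled ones. The Visit 6 assessment of a subject who skips the taper is also nominal. This stands, and it limits the point to ET and unscheduled records.

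Second, the gap before Day 83 may be only loose wording. The Day 78 contact lies in the Taper Phase, when a completer is still on drug. Read literally, even a completer's unscheduled score that day would have no row. The broader meaning of off treatment is therefore plausible. But the SAP does not define the term, and the broader meaning produces the collapse shown in step 2.

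Third, a reader might infer that the windows bias the endpoint toward no withdrawal effect. The documents do not support a direction: they give no time course of symptoms, and scores from subjects who stopped without taper could raise the Day 78 mean. Nor does the selection rule always keep the score furthest from stopping: Day 77 (1 day from target) beats Day 82 (4 days).

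Finally, the summary is descriptive in a trial the SAP calls exploratory, and individual data are listed. That bears on priority, but does not make the windows correct.

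**Conclusion.** The point holds for ET and unscheduled mCIWA-B records. For these, the Day 78 row pools off-drug scores from very different times since stopping (1 to 54 days in the Day 28 example, against about 7 days after Visit 4 for a completer). Taper scores before Day 83 have either no row or a single row for the whole taper. Rows from Day 83 ignore treatment status, Day 110 is assigned twice, and the status of the ET score is unclear. The Day 110 overlap needs no assumption; the no-row result depends on the literal reading of off treatment.

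The share of scores misplaced cannot be determined. A reader might take the early terminators' share of tapering subjects as the size of the problem. With 10 dropouts and 40 completers per arm, and an assumed 50% to 90% of completers entering the extension, that share is 10/(10 + 20) = 33% to 10/(10 + 4) = 71%. It rests on an assumed uptake and on every dropout supplying scores, and it counts subjects rather than misplaced records, so it is not the size of the defect. No hypothesis test, alpha level or power figure is affected. The change is worth making before database lock because the endpoint is named and the correction is cheap.

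**What to change.** In SAP 4.3, for ET and unscheduled mCIWA-B records of early terminators, replace the study-day windows of Table 9 with days since the first taper dose, or since the last dose if there is no taper, using dates in the EXPOSURE eCRF. In the same section:
- define off treatment, and say explicitly whether it includes taper drug;
- assign an ET score taken before the first dose reduction to Baseline;
- make the last two windows non-overlapping.

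Do not set the window centres yet. SAP Table 3 starts the taper at Day 71, while the dosing tables in the protocol (Table 4) and SAP (Table 1) list taper dose initiation at Days 78, 85 and 92. These passages must be reconciled first.

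A by-arm summary of the maximum change from baseline over taper and follow-up would be a useful but optional addition. The cost is SAP wording and slightly more programming, with no new data collection.

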5. STATISTICAL ANALYSIS METHODS

5.1. GENERAL CONSIDERATIONS

Descriptive statistical methods will be used to summarize the data from this trial, with statistical testing performed for the efficacy endpoints. Unless stated otherwise, the term "descriptive statistics" refers to number of subjects (N), number of observations (n), arithmetic mean, median, standard deviation (SD), coefficient of variation (CV%) (for concentration data only), first quartile (Q1), third quartile (Q3), minimum, and maximum for continuous data, and frequencies and percentages for categorical data. Certain figure presentations will include the standard error of the mean (SE). The term "treatment group" refers to treatment assignment: placebo and each active CVL 865 dose (7.5 mg BID, 25 mg BID). All data collected from subjects who sign the informed consent form, including screen failures, will be included in data listings. Unless otherwise noted, the data listings will be sorted first by treatment group and subject number and

The number and proportion of missing visits and key assessments due to COVID-19 control measures and the frequency of remote assessments performed due to COVID-19 restrictions will be tabulated by treatment, visit, and assessment as well as the overall number and proportion of subjects with any such missing visits, assessments, or remote visits in each treatment group.

The statistical analyses will be conducted with the SAS® software package version 9.4 or higher.

5.2. Populations for Analyses

The analysis populations are defined Table 10.

Population	Description	Analysis
All Screened Subjects	All Screened Subjects includes all subjects who signed the informed consent form.	Disposition
ITT	All randomized subjects	Disposition, Demographic and Baseline Characteristics
FAS	All randomized subjects who receive at least 1 dose of IMP. This will be the safety analysis set.	Safety analysis
mITT	All randomized subjects who receive at least 1 dose of IMP and have both baseline seizure frequency recorded in the eDiary with entry compliance $\geq 20\%$ and at least 1 post baseline entry in the seizure diary during maintenance phase.	Primary analysis set for efficacy
PK Analysis Set	All randomized subjects who receive at least 1 dose of IMP and have at least 1 measurable CVL-865 concentration	PK analysis

Table 10:Populations for Analysis

Abbreviations: FAS = full analysis set, IMP = investigational medicinal product, ITT = intent-to-treat, mITT = modified intent-to-treat, PK = pharmacokinetic.

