3.1. Efficacy Assessments

3.1.1. Seizure Frequency and Type (eDiary)

Subjects will record details regarding their seizures (frequency and type) in an eDiary. Any BZD use will also be recorded in the diary. Seizure frequency and type will be assessed based on information recorded by the subject in the eDiary.

Seizure frequency is defined as the total number of focal onset seizures over the analysis period of interest divided by the total number of days with no missing seizure counts in the corresponding period multiplied by 7. For cluster seizures, which are a group of seizures too numerous to count, the number of cluster episodes will be included as one seizure event. Unless otherwise specified, Seizure frequency will only be calculated for focal onset seizures, which include focal aware seizures without motor signs, focal aware seizures with motor signs, focal impaired awareness seizures and focal to bilateral tonic-clonic seizures.

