4.2. Analysis Periods

The start and end dates of each analysis period (following the study design) are used for the classification of efficacy data. The exact start and end of each of these periods is described for calculation purposes in Section 4.3. Seizure frequency and average daily dose for each analysis period will be calculated based on Table 3.

Table 3:	Definition of Analysis Periods for Seizure Frequency and Average Daily Dose
	Data

Analysis Period	Duration	Start Date	End Date
Baseline Period	~8 Weeks	The greater of: Study Day, -56 or Informed consent	Study Day, -1
Titration Phase	~2 Weeks	Study Day, 1	The lesser of: Day 15 (Visit 2) minus 1 or *Early termination (minus 1) or End of Treatment
Maintenance Phase	~8 Weeks	Day 15 (Visit 2)	The lesser of: **Day 71 (Visit 4) minus 1 or *Early termination (minus 1) or End of Treatment
Taper Phase	~3 Weeks	Day 71 (Visit 4) or *Early termination	End of Treatment

* If a subject experiences early termination from the study and continues to Taper Phase, end dates will be bound by early termination minus 1 while the start of Taper Phase will begin on the date of early termination. ** For subjects continues to Taper Phase from Maintenance Phase

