5.8.4.2. Impact of Low eDiary Entry Compliance

To evaluate the impact of subject's low compliance of eDiary entry on the results from the main analysis, a sensitivity analysis that treat these cases as missing at random will be performed. Specifically, if a subject has more than 50% of their diary entries missing over a period (baseline, maintenance, etc), the seizure frequency for that period will be treated as missing. Multiple imputations under missing at random assumption will be performed. The Markov chain method implemented in SAS PROC MI will be utilized based on the mITT population. The imputations will be performed on the logarithmic scale $(\ln(X+1))$, where X represents the 7 day average seizure frequency for a period, and back transformed to conform to the multivariate normality distribution and the imputed values will then be back transformed to the original scale. SAS PROC MI will be used to generate 10 possible imputed datasets using the following SAS code:

```
proc mi data=mcmc1 seed=SEED1 nimpute=10 minimum=0 out=Out1X;
mcmc chain=multiple displayinit initial=em(itprint);
var TRT y0 y;
run;
```

Where TRT is an indicator variable representing treatment with the two treatment groups of 'CVL-865 7.5 mg BID', 'CVL-865 25 mg BID' or 'Placebo', y represents $\ln(7 \text{ day average}$ seizure frequency over maintenance period + 1), y0 is $\ln(7 \text{ day average seizure frequency over}$ the baseline period+1), and SEED1 is a random number.

Each of these datasets will be analyzed using the same ANCOVA model through SAS PROC MIXED as described in Section 5.8.3. The results of the analyses of the datasets will be combined using PROC MIANALYZE to produce an inferential result.

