5.10.1. Second Key Secondary Estimand

The key research question for the second key secondary efficacy variable will be addressed with an estimand based on the following attributes:

- 1. Treatments: treatments as randomized regardless of the actual treatment received.
- 2. Target study population of interest: subjects in the modified intent-to-treat (mITT) population.
- 3. Endpoint (variable) of interest: 50% responder rate in the Maintenance Phase.

- 4. Population level summary of interest: the 50% responder rate in the Maintenance Phase relative to the baseline period between CVL-865 treated and placebo subjects.
- 5. Strategy for Intercurrent events (ICEs): a hypothetical strategy will be used to address intercurrent events (ICEs) of potential death, and treatment discontinuations. The data after treatment discontinuations will typically be missing or be treated as missing even if collected. These missing values as the result of ICEs of discontinuation will be assumed to follow the observed trajectory of the subject and thus the endpoint will include only eDiary based response data that occur before discontinuation of treatment. However, subjects with greater than 80% missing seizure diary entries will be treated as non-responders. It should be noted that the use of protocol defined rescue medication will not be considered as an ICE.

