5.10.2. Main Analytical Approach for Second Key Secondary Endpoint

The second key secondary endpoint, 50% responder rate, will be analyzed for the mITT population using a logistic regression model with effects for treatment and baseline seizure frequency. The binary outcome will be defined as having at least a 50% reduction in the maintenance phase relative to the baseline period or not having a 50% reduction. Odd ratios will be constructed for each CVL-865 treatment dose group compared with placebo and will be summarized with 90% confidence intervals. Subjects with greater than 80% missing seizure diary entries will be treated as non-responders for this analysis. Should a logistic regression model fail to converge, paired Fisher's exact tests will be used instead.

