5.10.3. Sensitivity Analyses

The sensitivity analyses to assess the impact of low eDiary compliance and that of discontinuation potentially related to treatment described in Section 5.8.4 for the primary estimand will also be performed for the second key secondary efficacy estimand. The 50% responder rate will be constructed off the results from the primary sensitivity analysis. This will be conducted for the two different sensitivity assessments will be conducted to assess the impact of this missingness (data are missing at random and data are not missing at random).

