5.11. Other Efficacy Analyses

5.11.1. Other Secondary Efficacy Endpoints

Other protocol-defined secondary efficacy endpoints will be summarized using descriptive statistics by treatment group and visit, if appropriate. Statistical analysis method for each endpoint is described below in Table 11. Statistical comparisons for each endpoint will be constructed without adjustment for multiple endpoints.

Table 11:	Summary of Other Secondary Efficacy Analyses

Endpoint	Analysis Population	Analysis Method
Seizure Freedom	mITT	Seizure freedom is defined as no seizures during the maintenance period. A logistic regression model with treatment as a fixed effect will be used. Odd ratios will be constructed for each CVL-865 treatment dose group compared with placebo and will be summarized with 90% confidence intervals. Should a logistic regression model fail to converge, paired Fisher's exact tests will be used instead.
Seizure Rate over Time	mITT	Seizure rate over time during the maintenance period will be analyzed using an MMRM. Only focal onset seizure will be included in this analysis. Data will be log-transformed using the convention ln(X+1), where X represents the seizure rate at each time point. Treatment group (CVL-865 7.5 mg, CVL-865 25 mg, or placebo), visit, and the interaction between treatment group and visit will be included as fixed factors in the MMRM, and log-transformed baseline rate will be included as a covariate. Subject will be included as a random effect, and an unstructured covariance structure will be used for the repeated measures. The difference between each CVL-865 level versus placebo at each visit will be estimated based on the LSMeans from the MMRM. The model estimated mean percent change from baseline and percent reduction versus placebo at each visit will be derived from back-transformed statistics the same way as described in Section 5.9.3 . A Mann-Whitney U test will also be used to compare each treatment level versus placebo at each visit.

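### Seizure freedom has no diary-completeness rule, the missing-diary rules state no denominator, and the protocol's all-available-data sensitivity analysis is absent from the SAP

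*SAP*

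**What the plan says.** - **Analysis set (SAP 5.2, Table 10).** mITT members have at least one dose, baseline diary compliance of 20% or more, and "at least 1 post baseline entry in the seizure diary during maintenance phase".
- **Maintenance Phase (SAP 4.2, Table 3).** It runs from Visit 2 (Day 15) to the earliest of the day before Visit 4 (Day 71), "Early termination (minus 1) or End of Treatment".
- **Seizure frequency (SAP 3.1.1).** The seizure count is "divided by the total number of days with no missing seizure counts in the corresponding period multiplied by 7". No minimum number of days is set.
- **Seizure freedom (SAP 5.11.1, Table 11).** "Seizure freedom is defined as no seizures during the maintenance period". Nothing is said about completion or diary days.
- **50% rule (SAP 5.8.4.2).** A period is set to missing and imputed under MAR when a subject has "more than 50% of their diary entries missing over a period (baseline, maintenance, etc").
- **80% rule (SAP 5.10.1).** "However, subjects with greater than 80% missing seizure diary entries will be treated as non-responders"; SAP 5.10.2 repeats it. Protocol 9.4.1 is stricter and counts any missing or incomplete seizure information as non-response.
- **Diary compliance (SAP 5.7.1).** Expected days are limited to actual participation and stop at the last dose.
- **Reach of the sensitivity analyses.** SAP 5.9.4 extends the missing-data analyses to the first key secondary endpoint, and SAP 5.10.3 says they "will also be performed for the second key secondary efficacy estimand". None is specified for seizure freedom.
- **Jump-to-reference (SAP 5.8.4.3).** It covers stops by Visit 3 for a seizure-class AE, subject withdrawal, lack of efficacy or loss to follow-up.
- **De facto analysis.** Protocol 9.4.1 commits to a sensitivity analysis on all available data. SAP 5.8.4 does not contain it, and SAP 5.8.2 sets post-discontinuation data aside. Protocol 8.1 has the diary kept daily through Visit 6.

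**The concern.** Taken together, these rules let seizure freedom depend on how long the diary ran. A subject who leaves after a day or two without a seizure enters mITT, scores RRatio -100, and counts as both a responder and seizure free. If stops unrelated to seizures are more common on active drug and fall early in Maintenance, these comparisons lean towards active with no drug effect.

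The safeguards do not clearly reach such a subject. Whether the 50% and 80% rules apply depends on an unstated denominator. A stop for a non-seizure AE is outside the jump-to-reference list. The analysis that would use diary data recorded after stopping is not planned. Disposition tables and diary listings would show that stops occurred, but not how far the estimates moved.

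**Working it through.** **1. The plan's own figures.** SAP 1.2 gives a difference of -20, SD 34, two-sided alpha 0.1, 80% power and 20% dropout. The normal formula gives n = 2 x (1.645 + 0.842)^2 x 34^2 / 20^2 = 35.7, so 36 per arm (37 by the exact t). With 40 evaluable per arm, exact power is 83.2%. The sample size reproduces and is not in dispute. The documents give no stop rates by arm and no stop timing; those below are assumptions.

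**2. Simple check.** The entry minimum is 8 seizures in 8 weeks, or 1 per week. With Poisson counts and no drug effect, P(no seizure in d days) = exp(-d/7): 86.7% for 1 day, 65.1% for 3, 36.8% for 7 and 0.03% for 56.

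**3. Simulation by diary length, no drug effect.** Assumed inputs: baseline rate lognormal, median 2.5 per week, log-SD 0.9; at least 8 baseline seizures; subject-level change lognormal, log-SD 0.65, with zero mean log change; Poisson counts. The 56-day RRatio SD is 33, against the planned 34.

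| Maintenance diary days | Mean RRatio | Seizure free | 50% responders |
|---|---|---|---|
| 1 | -44 | 59% | 60% |
| 3 | -20 | 31% | 36% |
| 7 | -10 | 13% | 27% |
| 28 | -3 | 1% | 21% |
| 56 | -2 | 0.2% | 19% |

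**4. Effect on a comparison.** Assume 20% of active and 5% of placebo subjects stop for reasons unrelated to seizures. The seizure-free rate in an arm is (stop share x stoppers' rate) + (remaining share x 0.2%). For days 1-3 the stoppers' rate is 43.6%:
- active: 0.20 x 43.6 + 0.80 x 0.2 = 8.9%
- placebo: 0.05 x 43.6 + 0.95 x 0.2 = 2.4%

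The RRatio bias is 0.15 x (stoppers' mean - (-1.6)). For days 1-3 it is 0.15 x (-30.7 + 1.6) = -4.4. False positives come from 20,000 simulated trials of 50 per arm; the rate with no stops is 9.8%.

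| Stop window (Maintenance days) | Seizure free, active vs placebo | RRatio bias | False positives (nominal 10%) |
|---|---|---|---|
| 1-3 | 8.9% vs 2.4% | -4.4 | 14.7% |
| 1-14 | 3.8% vs 1.1% | -1.8 | 11.1% |
| 1-55 | about 1.2% vs 0.5% | -0.6 | 10.3% |

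The RRatio bias depends on the baseline rate. In the same order of windows it is -7.1, -3.3 and -1.1 with every subject at 1 per week, and -2.5, -0.95 and -0.3 with a median of 7 per week. If a seizure triggers the stop and that day is counted, the sign reverses: 0.15 x (7.5 + 1.6) = +1.4.

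**5. Denominator.** Study Days 15 to 70 are 56 planned days. A subject who stops after 7 fully recorded days is 0/7 = 0% missing on actual participation, but 49/56 = 87.5% missing on planned days. On planned days the 80% rule catches 11 or fewer recorded days (45/56 = 80.4%; with 12 recorded it is 44/56 = 78.6%). The 50% rule catches 27 or fewer.

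**6. Jump-to-reference inputs.** The code in SAP 5.8.4.3 picks active subjects whose Maintenance or baseline value is missing. Every mITT member has a Maintenance value by definition, and the section does not say that the listed subjects' values are first set to missing.

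**The case against.** **The estimand is deliberate.** SAP 5.8.2, 5.9.2 and 5.10.1 adopt a hypothetical strategy on pre-discontinuation data, and protocol 9.4.1 likewise limits the primary analysis to such data. This stands. It is why the primary RRatio analysis and the main responder estimand should not be replaced.

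**Other analyses already check frequency.** The Poisson model in SAP 5.9.6 has an offset for diary days, so short diaries get little weight. In the worst case above (days 1-3) its mean log rate ratio was -0.003 (Monte Carlo SE 0.004), which is no bias. This stands for seizure frequency. The 50% compliance subgroup in SAP 5.8.5 is optional, and on actual participation a fully recorded early stopper is 100% compliant. Neither addresses seizure freedom.

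**The denominator can be inferred.** SAP 5.7.1 and Table 3 point to actual participation. That is a fair reading, but it is the one under which neither rule catches an early stopper.

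**The trial is exploratory.** SAP 5.4 uses this to justify no multiplicity adjustment. It does not explain a missing completeness rule or a dropped protocol analysis.

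**Stronger readings to avoid.** A reader might infer that the primary result is unreliable. With stops spread over Maintenance the RRatio bias is about -0.6, so that does not follow. A reader might also infer that the jump-to-reference code contradicts its text on placebo subjects, or that the status of Titration stoppers is undefined. The sentence introducing the code is cut off in the text reviewed, and the selection can be the active-arm step alone. The SAP's mITT definition, which excludes Titration stoppers, is its primary efficacy set. Subjects for this analysis are to be listed in SAP 9.5, which was not available for review.

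**Conclusion.** Two parts of the plan are wrong as written. Seizure freedom can be met by a diary of one or two days, with no completeness rule and no sensitivity analysis to show the effect. The de facto sensitivity analysis promised in the protocol is absent from the SAP without a stated reason. The unstated denominators and the narrow AE criterion in jump-to-reference are lesser gaps that are cheap to close.

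The size rests on assumed stop rates (20% vs 5%), stop timing and baseline rates. Under them the false seizure-freedom difference is 8.9 - 2.4 = 6.5 points when stops fall in days 1-3, 3.8 - 1.1 = 2.7 points for days 1-14, and about 0.7 points when spread over days 1-55. The direction holds only if stops unrelated to seizures are more frequent on active drug. The effect on the primary endpoint is small unless such stops cluster in the first days of Maintenance.

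**What to change.** Keep the primary RRatio analysis and the main responder estimand. Before unblinding:

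1. **Seizure freedom.** Do not count as seizure free any subject with more than 80% of the 56 planned Maintenance days missing, counting days after early termination as missing. Under the same assumptions the rates become 0.2% vs 0.2% (days 1-3), 0.4% vs 0.3% (days 1-14) and 0.4% vs 0.3% (days 1-55). The cost is a lower reported rate.
2. **Denominators.** State them for both rules. Run the SAP 5.8.4.2 imputation on 56 planned days. In simulation its bias was +0.1, +0.1 and 0.0 for the three windows (Monte Carlo SE 0.11), and its mean SE was 7.2, 7.2 and 6.9 against 8.0, 7.3 and 6.9 in the primary analysis. Report the responder rate on 56 planned days as a sensitivity analysis, which is closer to protocol 9.4.1. It counts against the arm with more early stops: with no drug effect the difference moves from +4.1 to -2.8 points (days 1-3) or from +0.5 to -0.4 (days 1-55). For that reason it should not replace the main analysis.
3. **De facto analysis.** Reinstate it on diary data from Study Days 15-70 regardless of discontinuation, noting that these include taper and off-drug days. The protocol already schedules this data collection.
4. **Jump-to-reference.** Add non-seizure AE discontinuations on or before Visit 3, and state that the Maintenance value is set to missing for listed subjects. The cost is a conservative analysis: 4-6% false positives at a nominal 10% in simulation.
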